Otoscope – a speculum-like instrument for visual examination of the external auditory meatus and tympanic membrane

Otoscopy – inspection of the external auditory meatus and tympanic membrane with an otoscope

Perilymph – cochlear fluid, found in the scala vestibule, scala tympani, and spaces within the organ of Corti, which is high in sodium and calcium and has an ionic composition that resembles cerebrospinal fluid

Perilymphatic fistula – abnormal passageway between the perilymphatic space and the middle ear, resulting in perilymph leakage at the oval or round window, usually caused by congenital defects or trauma

Potentially Hazardous Noise - Exposure to steady-state noise having an 8-hour TWA noise level of \geq 85dBA, or exposure to impulse/impact noise levels greater than 140 dB peak SPL, regardless of duration

Pure tone – Sound wave having only one frequency of vibration

Pure-tone air-conduction threshold – lowest level at which a pure-tone stimulus, presented through earphones is audible 50% of the time

Pure-tone average – PTA; average of hearing sensitivity thresholds to pure-tone signals at 500, 1000 and 2000 Hz

Pure-tone bone-conduction threshold – lowest level at which a pure-tone stimulus, presented via a vibrating oscillator, usually placed on the forehead or mastoid, is audible 50% of the time

Significant Threshold Shift (STS) - An average change of plus or minus 10 dB at 2000, 3000, and 4000 Hz, relative to the reference audiogram, in either ear, without age corrections (military definition)

Sound Pressure level – SPL; magnitude or quality of sound energy relative to a reference pressure, 0.0002dyne/cm² or 20 μ Pa

Threshold – level at which a stimulus or change in stimulus is just sufficient to produce a sensation or an effect that is perceived 50% of the time

Tinnitus – sensation of ringing or other sound in the head, without an external cause

Tympanogram –graph of the middle ear immittance as a function of the amount of air pressure delivered to the ear canal. Its purpose is to assess tympanic membrane and middle ear function

List of Figures

| | | |
|--------------|--|----|
| Figure 1/2 | Plasma Concentrations of D and L methionine | 9 |
| Figure 3/4 | Effects of experimental diets on the growth (A) and food consumption (B) of rats | 11 |
| Figure 5 | Protection from cisplatin-induced auditory threshold shift in rats..... | 12 |
| Figure 6 | Protection from cisplatin induced cochlear hair cell loss | 13 |

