4.3 Subject Selection

Six hundred military personnel enrolled in the Drill Sergeant School (DSS Candidates) at Ft. Jackson will be recruited for the study. This training requires that each Soldier fire approximately 500 rounds of M-16 weapons fire (156 dB SPL) within a 9-11 day period of weapons training with a possible additional makeup day if necessary to meet training requirements. Ft Jackson makes great efforts to prevent noise-induced hearing loss by means of physical hearing protection for all Soldiers. Every DSS Candidate in training at Ft Jackson is issued physical hearing protection, trained and required to use them at all times on the weapons range. Spent magazines are collected and tallied to document rounds fired.

Study subjects will be randomized to two equal arms: oral D-methionine (test drug) or flavor-matched placebo. All 600 subjects will receive either D-methionine (n = 300) or placebo (n = 300) twice daily for 18 days starting 3 days prior to the weapons training and ending 4 days after cessation of weapons training. Drug will be dispensed in the morning and in the evening at meal times. Drug logs will be kept for every subject, recording every dose taken or missed and whether or not battle plugs were used. Side effects will be assessed each time study drug is dispensed.

Soldiers routinely undergo pre-training audiology assessments that include pure tone threshold, otoscopy and tympanometry testing. Study participation will include the following additional audiology assessments: pre-post training pure tone threshold and tympanometry assessments. Pre- post training tinnitus

assessments are not routinely done and are a required assessment for this study which will be conducted by the audiologist and/or study coordinators.

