Experimental design consists of within-subjects serial testing in which baseline standard frequency (.5, 1, 2, 3, 4, 6, and 8 kHz) audiograms are initially acquired. By comparing similar measures obtained at the end of the study period to the relevant pre-exposure measure, reliable noise-induced changes in pure-tone hearing threshold can be identified. Thus, subjects will serve as their own control for identifying hearing change, relative to their baseline evaluation.

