10.2 Primary Efficacy Analysis

Two groups are planned in the randomized prospective design: the D-met and the placebo groups. The primary objectives, and their associated analyses, for this study are as follows:

1. To determine if there is a significant difference between the D-methionine and placebo treated groups in the average severity of documented side effects where severity is defined as the frequency of side effect multiplied by the intensity of the side effect. Repeated measures analysis of variance (ANOVA) will be utilized to determine significance.
2. To determine if there is a significantly reduced change in threshold hearing in each ear, adjusting for handedness, for the D-methionine group as compared to the placebo group at the tested audiometric frequencies. The tested audiometric frequencies will be 0.5, 1, 2, 3, 4, 6 and 8 kHz. Multi-way (2 groups x 7 frequencies) analysis of variance (ANOVA) with interaction effects and correction for multiple comparisons (Newman-Keuls) will be utilized to determine significance. Determination for early detection will be according to the American Speech-Language Hearing Association (ASHA, 1994) criteria of: 1) greater than or equal to a 20 dB change at any frequency, 2) greater than or equal to a 10 dB change at any 2 adjacent frequencies, or 3) loss of response at 3 consecutive frequencies where responses were obtained at baseline. To be considered significant ototoxicity, these changes must replicate within 24 hours (may be immediate) with no indication of middle ear abnormality. Subjects serve as their own controls for audiometric change, which is computed relative to baseline measures.
3. To determine if there is a significantly lower rate of STS (in either ear) for the D-methionine group as compared to the placebo group where STS is defined according to DOEHRSHC criteria as an increase of 10 dB or greater change (decrease in hearing) for the average of 2, 3 AND 4 kHz in

either ear. A significant negative STS (improved hearing) is defined as a decrease of 10 dB or greater change for the average of 2, 3 AND 4 kHz in either ear. An early warning shift STS (decrease in hearing) is defined as a 15 dB or greater change at 1, 2, 3 OR 4 kHz in either ear. Fisher's exact test will be utilized to determine statistical significance.

Secondary objective of the study is as follows:

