Audiologic assessments such as Threshold Testing, Otoscopy and Tympanometry Testing are routinely performed on all DSS Candidates within 3-6 months of the training period. Repeat audiological assessments will be performed at the study baseline and are considered study-related procedures. Tinnitus assessments will be performed at the study baseline and are considered to be study-related procedures. All audiologic assessments will be performed using the following standardized procedures. CPT [name], AuD, a licensed audiologist from the Army Hearing Program at Ft Jackson, will be responsible for overseeing all testing and for maintaining all audiologic data files for all subjects enrolled in the study.

2.) Otoscopy and Tympanometric Screening: Prior to each hearing test each Subject's ear will be examined with a Welch Allyn 3.5v Macroview otoscope to ensure that the ear canals are clear and the

tympanic membranes are normal in appearance. Tympanometry will be screened in each ear using pass-fail criteria of middle ear pressure: (pass is between +110 daPa and -160 daPa) and compliance: (Pass is between .2 and 1.4 ml) using the automated Interacoustics Handheld Middle Ear Analyzer MT10.

3.) Threshold Testing: Pure-tone threshold testing both at baseline and post-test (15-16 days after completion of weapons training) will be conducted utilizing the modified Hughson -Westlake procedure. Pure-tone air-conduction testing will be conducted at .5, 1, 2, 3, 4, 6, 8 kHz. Bone conduction testing will be conducted at 5, 1, 2, 3, 4 kHz if the air-conduction threshold at that frequency is 15 dB HL or greater. Audiological data is collected electronically via Interacoustic 629 clinical audiometers with insert earphones and TDH 39 earphones. Pure-tone threshold testing is conducted by the audiologists using DOEHRSHC standard test procedures using the modified Hughson Westlake procedure as follows: Initial descent towards threshold is accomplished in 10-dB steps. Beginning with the first non-response, level is increased by 5-dB for each non-response, and decreased by 10-dB after each correct detection response. Threshold is defined as the lowest level at which two responses are obtained out of three presentations on an ascending run. Test equipment, test environment, procedures, and personnel will meet all relevant DOEHRSHC, ASHA, AAA, ANSI and JC standards and guidelines.

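### The threshold-change analysis adjusts for neither the study baseline nor the routine pre-training audiogram, which costs a modest amount of precision but causes no bias

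*Combined protocol and SAP*

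**What the plan says.** Section 4.3 says that "Soldiers routinely undergo pre-training audiology assessments that include pure tone threshold, otoscopy and tympanometry testing". Section 11.1 (b, Source of Materials) gives coverage and timing: such assessments are "routinely performed on all DSS Candidates within 3-6 months of the training period". It then separates them from the trial's own tests: "Repeat audiological assessments will be performed at the study baseline and are considered study-related procedures".

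The trial plans one baseline. Under Section 5.5.3, baseline standard-frequency "audiograms are initially acquired", and the end-of-study audiogram is compared with them. Section 10.2 says: "Subjects serve as their own controls for audiometric change, which is computed relative to baseline measures". Threshold change is analysed by "Multi-way (2 groups x 7 frequencies) analysis of variance (ANOVA) with interaction effects", with handedness the only adjustment named. For STS, "Fisher's exact test will be utilized to determine statistical significance". Neither analysis gives the routine audiogram a role, and neither uses the study baseline as a covariate.

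**The concern.** Change is the final threshold minus the study baseline. Whatever error that one baseline test contains passes into the change score with weight one. Testing moves in 5-dB steps (Section 5.5.3), so the error is unlikely to be trivial.

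The study baseline as a covariate recovers only a little of this, because one reading cannot tell a good test day from good hearing. A second reading taken before the noise can help. If the study baseline is better than the routine test from some months earlier, part of the gap is probably test error, and that part predicts a spurious later shift. Such a reading is said to exist for every candidate. What is at stake is precision on threshold change, which is part of the primary efficacy endpoint in Section 4.2.1.

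**Working it through.** **The plan's own figure.** Section 10.1 powers the trial on STS only. Reading its 30% difference as relative, 38% falls to 0.38 × 0.70 = 26.6%. The pooled normal formula (two-sided 0.05, 80% power) gives 263 per arm against the stated 252; power at 252 is 78.3%. The point here does not depend on that gap. The plan has no precision calculation for threshold change.

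**Model for threshold change** (one ear, 2-3-4 kHz mean). True hearing has SD b, each test has error SD e, the true shift within an arm has SD s, and drift since the routine test has SD d. All are taken as independent.

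- Change = shift + final-test error − baseline error, so Var = s² + 2e².
- Variance removed by the study baseline alone: e⁴ / (b² + e²).
- Variance removed by study baseline and routine test together: e⁴(b² + d² + e²) / [(b² + e²)(b² + d² + e²) − b⁴].
- Worth of the routine test in subjects: ratio of the two residual variances, minus 1.

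**Inputs.** The documents give none of these SDs. Assumed ranges in dB: b 8-12, e 2.5-3.5, s 4-6, d 1.5-3, with d 4-5 as a less favourable case.

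**Mid-range example** (b 10, e 3, s 5, d 2):

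- Var(change) = 25 + 18 = 43.
- Study baseline alone: 81/109 = 0.74, a cut of 1.7%.
- Both: 81 × 113 / (109 × 113 − 10,000) = 9,153/2,317 = 3.95, a cut of 9.2%.
- Gain from the routine test: (43 − 0.74)/(43 − 3.95) = 42.26/39.05 = 1.082, or about 8% more subjects.

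**Over the ranges:**

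| Drift SD (dB) | Cut, study baseline only | Cut, both | Gain from routine test, as extra subjects |
|---|---|---|---|
| 1.5-3 | 0.5-4.9% | 4.0-15.4% | 3.3-14.3% (17-72 of 504) |
| 4-5 | 0.5-4.9% | 2.5-11.6% | 1.9-8.9% (9-45 of 504) |

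A two-ear simulation over the first set of ranges gave a 3-14% cut with both covariates and an added gain of 13-65 subjects, in line with the closed form. All of this concerns the 2-4 kHz mean; nothing was computed for 0.5, 1, 6 or 8 kHz.

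**STS.** Exact power at 252 per arm, 38% v 26.6%, two-sided 0.05, is 75.6% for Fisher's test and 78.4% for an unadjusted logistic (Wald) test. Logistic power, simulated with 4,000 trials in each of three scenarios:

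| Scenario | No covariate | Study baseline | Both | Added by routine test |
|---|---|---|---|---|
| 1 | 0.783 | 0.786 | 0.795 | 0.9 points |
| 2 | 0.780 | 0.785 | 0.812 | 2.7 points |
| 3 | 0.798 | 0.800 | 0.806 | 0.6 points |

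The simulation error of one such power is √(0.8 × 0.2 / 4,000) = 0.6 points, so two of the three gains are close to it. Leaving Fisher's test for the unadjusted logistic test gains 78.4 − 75.6 = 2.8 points without any extra audiogram.

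**The case against.** The strongest reply is that STS carries the sample size, that Fisher's test cannot take a covariate, and that even a logistic analysis gains little. Every SD is assumed. The routine test may be up to six months old, and the documents do not say that it used the study audiometers, the 24-hour noise-avoidance rule or 8 kHz. A fresh, standardised baseline is a legitimate choice. Section 11.1 describes the routine test to separate it from study procedures and does not promise the data to the trial.

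Nearly all of this stands, and it limits the point to threshold change. It does not remove the point: that measure is a primary efficacy measure, and its model contains no pre-noise covariate at all.

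A reader might infer more than the documents support:

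- *That the treatment comparison is biased.* Baseline test error has the same distribution in both arms under randomisation, so the mean difference in change is unbiased.
- *That the trial loses material STS power.* The figures above do not show that.
- *That adjusting for the study baseline is useless.* It removes a little, 0.5-5% here.
- *That the two pre-noise tests should be averaged into a new baseline.* That would redefine change and STS, and the averaged baseline is less noisy only while (2e² + d²)/4 < e², that is, while d² < 2e².
- *That the routine test is already in use*, because the Definitions list ties STS to a reference audiogram. The list does not say which test that is, and Section 10.2 refers to baseline measures.

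**Conclusion.** The point holds as an optional gain in efficiency. Section 10.2 adjusts threshold change for neither the study baseline nor an existing earlier audiogram, so some precision is lost on a primary efficacy measure. No inference is invalid.

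Under the assumed SDs, the routine test is worth roughly 2-14% more subjects for threshold change, and less as drift grows. For STS it is worth about 1-3 power points in an adjusted model and nothing in the planned test. These sizes rest on assumed error, spread, shift and drift for the 2-4 kHz mean, and on the routine records being retrievable. The direction for threshold change needs only that the routine test carries some information about hearing before the noise.

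**What to change.** - **Sections 4.3 and 5.5:** record the date of each subject's routine audiogram and its thresholds per ear, at whichever study frequencies it contains.
- **Section 10.2, threshold change:** add the study baseline and the routine threshold as covariates, matched by ear and frequency (or the 2-3-4 kHz mean when the 2-4 kHz average is analysed). Use a missing indicator where the routine value is absent.
- **Reference for change and STS:** keep the study baseline, and make the reference audiogram in the Definitions list say so.
- **STS:** label any covariate-adjusted analysis supportive and report it as a standardised risk difference. A logistic odds ratio is conditional on the covariates, whereas Section 10.2 asks for intervals on differences.

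The cost is retrieval of about 600 records, whose access and completeness are not documented, and a sentence or two in Section 10.2. An older test, or one made with other equipment, other noise-avoidance rules or fewer frequencies, lowers the gain. It does not bias the randomised comparison, because the routine test predates randomisation and serves only as a covariate.

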4.6 Inclusion of Women and Minorities

Both men and women and members of all races and ethnic groups are eligible to participate in this study. No exclusion based on race or ethnicity will be used. Although all eligible and consenting women and minorities will be included in this study, the demographic information for the study site suggests that this population is typically 87% male and 13% female. Approximately, 14% are Hispanic or Latino, 1 % American Indian or Native Alaskan, 3 % Asian, 1 % Native Hawaiian or other Pacific Islander, 17% Black or African American and 74 % White.

4.7 Subject Withdrawals

Every effort will be made to ensure that subjects complete the study through the 30 day study period, consistent with provisions of informed consent and good clinical judgment with respect to safety. The following are potential reasons to terminate the participation of a subject in the study:

1. The subject's health would be jeopardized.
2. Lost to follow-up: the subject fails to return to the site for scheduled visits and does not respond to reminders or attempts to contact.

3. Withdrawal of consent: subject decides to stop participation for any reason or is unable to complete the study as described in the protocol. The investigator will make a reasonable effort by person-to-person or telephone interview if allowed by the withdrawn volunteer, to ascertain the subject's reason(s) for withdrawal.

The reason for withdrawal will be captured on the appropriate case report form (CRF) and the medical monitor will be informed of removal or early withdrawal of a subject from the study.

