4.8 Subject Replacement

If a subject receives any part of the investigation treatment, and must discontinue treatment for any reason, they will not be replaced.

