10.0 STATISTICAL CONSIDERATIONS

10.1 Sample Size Justification

Based upon the results of the 2004 study at the Marine Corps Recruit Depot (MCRD), it is estimated that the rate of significant threshold shift (STS) will be approximately 38% for the control (placebo) group. A power analysis incorporating a 95% confidence level ($\alpha = 0.05$), 80% power, a 1:1 ratio (placebo to D-methionine), and a detectable difference in threshold shift rates of 30% yields a required sample size of 252 subjects for each of the two arms (placebo and D-methionine) of the study. Thus a total of 504 subjects need to complete the study. Assuming an attrition rate of 20% in each arm over the course of the study, a total of 600 subjects will need to be enrolled.

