13.0 STUDY TIMELINE

Up to 16 Drill Sergeant School (DSS) classes are scheduled each year and each class includes approximately 100 candidates. To meet the enrollment goal of 600 subjects it is anticipated that approximately 50 subjects per class will enroll. An estimated 504 subjects are needed to complete all follow-up assessments (252 subjects per group) to detect significant differences for the primary outcome measures. The five year proposed timeline is provided in the table below. Recruitment will begin by the fourth quarter of Year 3. New DSS Training Sessions begin approximately every two-three weeks. Approximately 50 subjects are expected to enroll per session X 13 sessions. Please note that that the protocol includes enrolling the first group and completing all procedures and data collection on that group prior to additional treatment groups. The study team will then review that process before proceeding to the next group. After all procedures are documented to be flowing smoothly recruitment will proceed from each group of DSS students with classes starting every 2-3 weeks and thus, recruitment and data collection will overlap.

| | Mar 1 2011 | | | | Mar 1 2012 | | | | Mar 1 2013 | | | | Mar 1 2014 | | | | Mar 1 2015* | | | |
|------------------------------|------------|---|---|---|------------|----|----|----|------------|----|----|----|------------|----|----|----|-------------|----|----|----|
| Years | 1 | | | | 2 | | | | 3 | | | | 4 | | | | 5 | | | |
| Months | 1 | 3 | 6 | 9 | 12 | 15 | 18 | 21 | 24 | 27 | 30 | 33 | 36 | 39 | 42 | 45 | 48 | 51 | 54 | 57 |
| Site Visit | x | | x | | | x | | | x | | | | | | | | | | | |
| Study Team Meetings | x | | x | x | x | x | x | x | x | x | x | x | x | x | x | x | x | | | |
| Prepare and File IND | x | | x | x | x | x | x | | | | | | | | | | | | | |
| IRB Submission/ Approval | | | | | | x | x | x | x | x | | | | | | | | | | |
| Order Study Drug | x | | | | | | | | | | | | | | | | | | | |
| Formulate Study Drug | x | | | | | | | | | | | | | | | | | | | |
| Finalize Recruitment Plan | | | | | | | | | | | | | | | | | | | | |
| Hire Study Staff | x | | | | | | | | x | x | x | | | | | | | | | |
| Site Training | | | | | | | | | | x | x | x | | | | | | | | |
| Finalize MOP | | | | | | | | | x | x | x | | | | | | | | | |
| Pilot | | | | | | | | | | | x | x | | | | | | | | |
| Recruit/Enroll Subjects | | | | | | | | | | | | x | x | x | x | x | x | x | | |

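### Sections 4.7 and 4.8 do not separate stopping study drug from leaving the study, so the Day 29-32 audiogram may be missing in subjects who stop drug

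*Combined protocol and SAP*

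**What the plan says.** Section 4.7 opens with a retention aim: "Every effort will be made to ensure that subjects complete the study through the 30 day study period". It then introduces its list with "The following are potential reasons to terminate the participation of a subject in the study". The first reason is that the subject's "health would be jeopardized". The second is loss to follow-up. The third is withdrawal of consent, defined as the case where the "subject decides to stop participation for any reason or is unable to complete the study as described in the protocol". The investigator is to try to learn why a subject withdrew, and the reason goes on a CRF. The section does not mention study drug.

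Section 4.8 covers a subject who has received some study treatment and "must discontinue treatment for any reason, they will not be replaced". It says nothing about follow-up.

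Other relevant places:
- Section 4.3 has taken and missed doses logged for every subject, and Section 7.6 reconciles compliance against that log.
- Section 6.3 schedules the post-study audiogram, tympanometry and tinnitus questionnaires on Days 29-32, with no condition that the subject is still on drug.
- The schedule in Section 12.0 has no early-termination visit.
- Section 10.1 states "Thus a total of 504 subjects need to complete the study". Section 13.0 describes the same 504 as those who complete the follow-up assessments.
- Section 10.2 names Fisher's exact test for STS but gives no efficacy analysis set and no missing-data rule. The one exclusion from analysis that I find is in Section 9.2, for an abnormal final tympanogram. The set of all subjects with at least one dose, in Section 8.4.1, is for the adverse event tables.

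**The concern.** The trial asks whether giving D-methionine prevents permanent hearing loss from required weapons training. A soldier who stops the suspension still fires about 500 rounds, so his hearing outcome exists and can be measured at a visit already planned. The text gives site staff no status for stopping drug while staying in follow-up. Someone who cannot finish the 36 doses (18 days, twice daily) could reasonably be filed under the third reason in Section 4.7, as if he had withdrawn consent, and then not be called back.

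If that happens, the comparison drifts from all randomised subjects towards those who tolerated the drug. Section 8.4.1 names gastrointestinal symptoms as the expected adverse events, so the loss may not be the same in the two arms.

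**Working it through.** **Inputs.** From Section 10.1: placebo STS rate 38%, a detectable difference of 30%, 80% power, alpha 0.05, 252 completers per arm, 20% attrition in each arm, 600 enrolled. Two-sided testing is my assumption, because sidedness is not stated.

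**Reading the 30%.** As a relative reduction, the D-methionine rate is 0.38 x 0.70 = 0.266, a difference of 11.4 points. The pooled normal approximation gives n = [1.960 x sqrt(2 x 0.323 x 0.677) + 0.842 x sqrt(0.2356 + 0.1952)]^2 / 0.114^2 = 263 per arm. The stated 252 is not reproduced exactly, but power at 252 is 78.3%. As an absolute reduction (38% to 8%), n would be 30 per arm. I therefore use the relative reading. The gap between 263 and 252 is a separate matter and does not affect this point.

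**What cannot be computed.** The documents do not split the 20% attrition into drug discontinuation, loss to follow-up and refusal. I show missing fractions m of 5%, 10% and 20% in each arm. These are assumptions, with the plan's own figure as the top of the range.

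**Step 1: bounds.** Suppose the subjects with an audiogram show 38% v 26.6%. The true difference among all randomised (placebo minus D-methionine) is (1 - m) x 11.4 points, plus or minus 100m points. The extremes arise when every missing subject in one arm has an STS and none in the other does.

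| m per arm | (1 - m) x 11.4 | Lowest | Highest |
|---|---|---|---|
| 5% | 10.8 | 5.8 | 15.8 |
| 10% | 10.3 | 0.3 | 20.3 |
| 20% | 9.1 | -10.9 | 29.1 |

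A negative value means more STS on D-methionine.

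**Step 2: a single plausible case.** Suppose subjects who stop D-methionine get no benefit and have the 38% placebo rate. The all-randomised D-methionine rate is (1 - m) x 26.6% + m x 38%, which is 27.2%, 27.7% and 28.9%. The all-randomised effect is 10.8, 10.3 and 9.1 points. A comparison of completers still shows 11.4, so it overstates the effect by 1/(1 - m) - 1, which is about 5%, 11% and 25%.

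**Step 3: type I error.** Take a null drug with 38% STS in both arms, and assume 50% or 60% STS among those lost. If 20% are lost on D-methionine and 10% on placebo, the remaining rates are (0.38 - 0.20p)/0.80 and (0.38 - 0.10p)/0.90. For p = 0.5 these are 35.0% v 36.7%, and for p = 0.6 they are 32.5% v 35.6%. The false benefit is 1.7 or 3.1 points. By Fisher's exact test at 240 v 270 subjects, the two-sided error is 6.1% or 10.3%, against 4.5% without the bias. With equal loss and the same p in both arms, the two rates are identical and there is no bias.

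**The case against.** Several points on the other side stand. Section 4.7 never mentions study drug, and Section 4.8 treats discontinuation as a separate matter. A reader might infer that the protocol equates stopping drug with leaving the trial and that the audiogram is therefore lost. The documents do not say that. Missed doses are only logged and are nowhere made a reason to exit. Section 6.3 puts no on-drug condition on the Day 29-32 tests, and no section cancels them.

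A reader might also infer that Sections 10.1 and 13.0 define a completers analysis. They do not. Both are sample-size statements, and Section 13.0 counts completed follow-up, so a subject who stops drug but attends Day 29-32 counts.

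The size is easily overstated. Charging the whole 20% to this gap is not supported, because some of it will be loss to follow-up or real refusal, which no wording recovers. The type I error figures need unequal loss, whereas Section 10.1 assumes 20% in each arm.

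Finally, the CRFs were moved to separate documents and the consent pages are not available here. A field separating drug stopped from study stopped may already exist.

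None of this closes the gap. The retention aim in Section 4.7 is not an instruction to test subjects who stop drug. Section 6.3 speaks of subjects, and someone whose participation has been terminated may no longer be treated as one. Classing inability to complete as withdrawn consent points staff the wrong way.

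**Conclusion.** The concern holds as a gap with a misleading clause, not as a rule that discards data. Sections 4.7 and 4.8 leave open whether subjects who stop drug are followed, and Section 10.2 leaves open how they are analysed. The primary outcome may be missing in them although their exposure continues.

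Assuming 38% v 26.6%, the consequence is modest if few outcomes are lost: at 5% per arm the whole range stays in favour of D-methionine. At 10% the lower limit is close to zero, and at the plan's full 20% the direction is no longer secured. If stoppers get no benefit, the completer figure overstates the effect by about 5% to 25% over the same range.

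Inflated type I error should not be claimed as a consequence of the plan as written. It requires loss that differs by arm, which is possible given the expected gastrointestinal events but is not assumed. This is worth changing because the remedy is cheap and uses an existing visit.

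**What to change.** - In Section 4.7, define discontinuation of study drug separately from withdrawal from the study.
- Delete the second limb of the withdrawal-of-consent item, the one about inability to complete, so that the item covers only a subject's own decision to stop taking part.
- State that any randomised subject who stops drug, for whatever reason, is still asked to attend the Day 29-32 audiogram, tympanometry and tinnitus questionnaires unless he or she declines follow-up.
- State in Section 10.2 that such subjects are analysed in the arm to which they were randomised.

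This does not touch when or why drug is stopped.

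**Cost.** Protocol wording, and one CRF field for drug stopped v study stopped if none exists. The visit, staff and equipment are already planned. The estimated effect may be somewhat smaller because subjects off drug count. In the Step 2 case, with all 300 per arm followed, power by normal approximation is 80.9%, 76.4% and 65.9% at 5%, 10% and 20% stopping. A comparison of completers gives a nominal 83.1%, 81.0% and 76.3%, but for a larger effect that does not describe everyone randomised.
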